6.3 Dose-Modification Guidelines

The ixazomib dose reduction steps are 3 mg \rightarrow 2.3 mg \rightarrow 1.5 mg (Table 4-1), and the dose modification guidelines are provided in the IB and Table 4-2 and 4-3 below.

Treatment monitoring and dose modifying strategies. Liver Function Tests will be conducted twice a month for the first 3 months, then monthly thereafter. The Complete Blood Count (CBC) will be checked monthly. They will undergo clinical evaluation at baseline and every three months until the end of the study. Ixazomib dose modifying strategies will be implemented as outlined in the IB.

6.3.1 Recommended Ixazomib Criteria for Beginning or Delaying a Subsequent Treatment Cycle & Dose Modifications for Treatment Associated Toxicity

Treatment with ixazomib will use a cycle length of 28 days. For a new cycle of treatment to begin, the patient must meet the following criteria:

- ANC must be $\geq 1,000/\text{mm}^3$.
- Platelet count must be $\geq 75,000/\text{mm}^3$.
- All other nonhematologic toxicity (except for alopecia) must have resolved to \leq Grade 1 or to the patient's baseline condition

If the patient fails to meet the above-cited criteria for initiation of the next cycle of treatment, dosing should be delayed for 1 week. At the end of that time, the patient should be re-evaluated to determine whether the criteria have been met. If the patient continues to fail to meet the above-cited criteria, delay therapy and continue to re evaluate. The maximum delay before treatment should be discontinued will be 3 weeks or at the discretion of the Principal Investigator.

For dosing recommendations upon recovery, refer to Table 642 and Table 4-3.

Table 4-1 Ixazomib Dose Adjustments

| Dose Level | Dose (mg) |
|---------------|-----------|
| Starting Dose | 3.0 mg |

| | |
|-----------------------------|-------------|
| First Level Dose Reduction | 2.3 mg |
| Second Level Dose Reduction | 1.5 mg |
| Third Level Dose Reduction | Discontinue |

Once ixazomib is reduced for any toxicity, the dose may not be re-escalated.

Dosage adjustments for hematologic toxicity are outlined in Table 4-2.

Table 4-2 **Ixazomib** Dose Adjustments for Hematologic Toxicities

| Criteria | Action |
|---|--|
| Dose Modifications for Treatment Cycles | |
| 
 Delay of > 2 weeks in the start of a subsequent cycle due to lack of toxicity recovery as defined in Section 6.3.1 ANC < $1.0 \times 10^9/L$, platelet count < $75 \times 10^9/L$, or other nonhematologic toxicities > Grade 1 or not to the patient's baseline condition | 
 Hold ixazomib until resolution as per criteria Section 6.3.1. Upon recovery, reduce ixazomib 1 dose level. The maximum delay before treatment should be discontinued will be 3 weeks or at the discretion of the PI. |

Treatment modifications due to ixazomib-related AEs are outlined in Table 4-3.

Table 4-3 **Ixazomib** Treatment Modification (Delays, Reductions, and Discontinuations) Due to Adverse Events (Non-Hematologic Toxicities)

| Adverse Event (Severity) | Action on Study Drug | Further Considerations |
|---|---|---|
| Peripheral Neuropathy: | | |
| Grade 1 peripheral neuropathy | 
 No action | Grade 1 signs and symptoms: asymptomatic; without pain or loss of function; clinical or diagnostic observations only [14] |
| New or worsening Grade 1 peripheral neuropathy with pain or Grade 2 | 
 Hold study drug until resolution to Grade ≤ 1 or baseline | Grade 2 signs and symptoms: Moderate symptoms; limiting instrumental activities of daily living (ADL) [14] |

Table 4-3 Ixazomib Treatment Modification (Delays, Reductions, and Discontinuations) Due to Adverse Events (Non-Hematologic Toxicities)

| Adverse Event (Severity) | Action on Study Drug | Further Considerations |
|--|---|--|
| New or worsening Grade 2 peripheral neuropathy with pain or Grade 3 | 
 Hold study drug until resolution to Grade \leq 1 or baseline Reduce study drug to next lower dose upon recovery | Grade 3 signs and symptoms: severe symptoms; limiting self-care ADL; assistive device indicated [14] |
| New or worsening Grade 4 peripheral neuropathy | 
 Discontinue study drug | |
| Grade 2 Rash | 
 Symptomatic recommendations as per section 6.7 | The investigator and project clinician may discuss considerations for dose modifications and symptom management. |
| Grade 3 nonhematologic toxicity including hepatic and cardiac judged to be related to study drug If not recovered to < Grade 1 or baseline within 4 weeks | 
 Hold study drug until resolution to Grade $<$ 1 or baseline Reduce study drug 1 to next lower dose upon return to < Grade 1 or baseline | Symptomatic recommendations noted in Section 6.7 |
| Subsequent recurrence Grade 3 that does not recover to < Grade 1 or baseline within 4 weeks | 
 Hold study drug until resolution to Grade $<$ 1 or baseline Reduce study drug to next lower dose | Monitor closely, take appropriate medical precautions, and provide appropriate symptomatic care |
| Grade 4 nonhematologic toxicities including hepatic and cardiac judged to be related to study drug | 
 Consider permanently discontinuing study drug | Exceptions are cases in which the investigator determines the patient is obtaining a clinical benefit |

Once ixazomib is reduced for any toxicity, the dose may not be re-escalated.

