- Liver Function tests will be conducted twice a month (+ 6 /- 3 days) for the first 3 months, then monthly thereafter. The complete blood count (CBC) will be checked monthly. cPRA, BAFF/APRIL, DSA and antibodies will be checked every three months (5 times total). Bone marrow aspirates will be collected at the beginning and at one of the following endpoints: one month (+6, - 3 days) after the end of the 12 month study, cPRA decline > 20%, time of transplant, or time of subject withdrawal from the study. ECG and echocardiograms will be done at the baseline, 6 months, and end of the study visits.
- During the first three months of study participation, the bi-weekly Liver Function Tests may be done at the subject's local lab. The local lab will process the sample and send the result to the study team.
- Additional visits may be required if the subject has to hold treatment and needs to return to the clinic for blood draws to confirm eligibility to continue. Please see Table 4-3, Dose Adjustments for Hematologic Toxicities for dose adjustment plan.
- Data on acute rejection, graft and patient survival will be collected for six months after surgery for those subjects who receive a successful kidney transplant.

[figure not shown]
Unscheduled Visits: Subjects may have unscheduled visits due to dose adjustments based on lab results, an acute illness of undetermined cause, for other reasons, or at the discretion of the Investigator. Unscheduled visits may include any of the following procedures;

- Adverse Event Assessment
- Medication History
- Drug Accountability
- Physical Exam
- Vital Signs (Temperature, Pulse, Respirations, Blood Pressure)
- Lab work (CBC, LFTs, cPRA, BAFF/APRIL, DSA Antibodies)
- Bone Marrow Aspiration

Early Termination Visit: All subjects who end study participation prior to the end of the scheduled treatment will undergo an early termination visit within one week from study discontinuation. The early termination visit will consist of the following procedures;

- Adverse Event Assessment
- Medication History
- Drug Accountability
- Physical Exam
- Vital Signs (Temperature, Pulse, Respirations, Blood Pressure)
- Lab work (CBC, LFTs, cPRA, BAFF/APRIL, DSA Antibodies)
- Bone Marrow Aspiration (bone marrow aspiration will be done within 48 hours of transplant)

Figure 1. Study Overview Diagram

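### Section 6.3.1, Table 4-2 and Table 4-3 give unreconciled dosing instructions for Grade 2 rash, Grade 2 neuropathy without pain and slow-resolving Grade 3 toxicity, and reductions cannot be undone

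*Combined protocol and SAP*

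**What the plan says.** All of this is in Section 6.3 of the combined protocol and SAP unless stated otherwise.

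- **Section 6.3.1** requires neutrophils, platelets and all nonhematologic toxicity other than alopecia to meet set limits before a new cycle starts; for nonhematologic toxicity the limit is Grade 1 or baseline. If they are not met, "dosing should be delayed for 1 week", followed by re-evaluation. Treatment stops after a maximum delay of 3 weeks, subject to the investigator's discretion. For the dose after recovery the section refers to the tables.
- **Table 4-2**, introduced as covering hematologic toxicity, opens its criteria cell with "Delay of > 2 weeks in the start of a subsequent cycle due to lack of toxicity recovery as defined in Section 6.3.1". It continues with low neutrophils, low platelets, or "other nonhematologic toxicities > Grade 1 or not to the patient's baseline condition". The action is to hold and then "Upon recovery, reduce ixazomib 1 dose level", with the same 3-week maximum and the same discretion.
- **Table 4-3**, for nonhematologic events, answers "New or worsening Grade 1 peripheral neuropathy with pain or Grade 2" with a hold until resolution and no reduction. The next row, for Grade 2 with pain or Grade 3, adds a reduction. For Grade 2 rash the only listed action is "Symptomatic recommendations as per section 6.7"; the side column leaves dose changes open for discussion. For Grade 3 nonhematologic toxicity not recovered within 4 weeks, it holds and then reduces.
- **Tables 4-1 and 4-3** add that "Once ixazomib is reduced for any toxicity, the dose may not be re-escalated". The steps in Table 4-1 are 3.0 mg, 2.3 mg, 1.5 mg, then discontinuation.

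**The concern.** One clinical picture should lead to one action. Here a nonhematologic trigger sits inside a table labelled hematologic, and it overlaps rows of the table written for nonhematologic events. Staff who follow different passages can put the same patient on different doses, or stop treatment in one case and not in the other.

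This reaches the analysis. Section 7.1 analyses discontinuation due to adverse events, as the primary safety endpoint, with an exact binomial test. There are 10 patients, and those withdrawn are not replaced (Section 6.12). Because a reduction is permanent, an early difference in reading carries through every later cycle. Part of the delivered dose, and possibly of the discontinuation count, would then reflect which passage was applied rather than how the drug was tolerated. Distal neuropathy, one of the toxicities named in the primary objective, is directly involved.

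**Working it through.** The plan states no figure on this point to reproduce. The check sets the rules side by side and then sizes one case.

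**Step 1. Conflicts that hold on either reading of Table 4-2**

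| Event | Table 4-3 | Section 6.3.1 and Table 4-2 |
|---|---|---|
| Grade 2 rash at a cycle start | Symptomatic care; dose change only a matter for discussion | Next cycle blocked until Grade 1 or less or baseline; 3-week maximum or investigator discretion; one-level reduction on recovery if the delay exceeded 2 weeks |
| Grade 2 neuropathy without pain, cycle delayed more than 2 weeks | Hold; no reduction listed | One-level reduction on recovery |
| Grade 3 nonhematologic toxicity, recovery after more than 4 weeks | Hold, then reduce | Discontinue after a 3-week delay, unless the investigator decides otherwise |

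**Step 2. The Table 4-2 criteria cell**

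- One criterion: a delay of more than 2 weeks, with the counts and grades defining what counts as not recovered.
- Two triggers: the delay, or any of the listed counts and grades.

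Assuming weekly re-evaluation (Section 6.3.1 fixes only the first week):

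| Delay | One criterion | Two triggers |
|---|---|---|
| 1 week | no reduction | reduction |
| 2 weeks | no reduction | reduction |
| 3 weeks | reduction | reduction |

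Under two triggers the 2-week condition adds nothing, since any delay for non-recovery already meets the second trigger. The wording about not having returned to baseline also fits a definition of non-recovery. One criterion is therefore the better reading. The text available here does not show the cell's bullets, so the layout does not settle it. The choice decides whether a low count that recovers within a week costs a permanent dose level.

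**Step 3. Size of one case**

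Inputs: 12 cycles of 3 doses (Section 6.2); 3.0 mg starting dose and 2.3 mg first reduction (Table 4-1); no re-escalation. Assumptions: one Grade 2 neuropathy event without pain delays cycle 2 by three weeks, then resolves; all other doses are given, so the delay postpones doses rather than losing them.

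- Planned, and under Table 4-3: 12 x 3 x 3.0 = 108 mg.
- Under Table 4-2: cycle 1 gives 3 x 3.0 = 9 mg; each later cycle gives 3 x 2.3 = 6.9 mg; total 9 + 11 x 6.9 = 84.9 mg.
- Ratio: 84.9 / 108 = 79%.

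**Step 4. Effect on the safety variable**

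One patient in 10 is 1/10 = 10 percentage points. A single reduction does not move the rate. It moves when the passages disagree on stopping: a Grade 2 rash or a Grade 3 toxicity still unresolved at 3 weeks meets the maximum delay in Section 6.3.1 and Table 4-2, while the matching Table 4-3 rows contain no such limit.

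**Step 5. Pointers**

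- Section 4.1 says "Please see Table 4-3, Dose Adjustments for Hematologic Toxicities for dose adjustment plan", and Section 9.1 repeats it. Table 4-3 is the nonhematologic table and has no rows for counts.
- Section 6.3.1 cites a Table 642, which does not exist.
- Table 4-3 cites Section 6.7 for symptomatic care; that section covers preparation and dispensing.

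**The case against.** The strongest defence is that the passages form a sequence: Section 6.3.1 delays, then sends the reader to the tables for the dose on recovery. Table 4-2 acts only after more than 2 weeks, and the investigator may override the 3-week maximum. The rash row in Table 4-3 allows dose changes to be discussed. Section 6.3 also refers to the investigator's brochure, which is not available here. Drug is dispensed one cycle at a time after review of adverse events and laboratory results, at a single centre, which limits inconsistent application.

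Much of this stands, and it rules out stronger readings that a reader might infer:

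- *That Table 4-2 reduces the dose for any nonhematologic toxicity above Grade 1 or any low count.* This drops the 2-week condition and needs the weaker two-trigger reading. On the better reading, Grade 2 neuropathy without pain that resolves in a week is not reduced under either table.
- *That the two tables conflict on low counts.* Table 4-3 has no rows for counts; that ambiguity lies inside Table 4-2.
- *That short events would drive a patient to discontinuation.* Three brief events at the starts of cycles 2, 4 and 6 would leave 9 + 2 x 6.9 + 2 x 4.5 = 31.8 mg (29% of 108 mg), but only on the weaker reading and with three assumed events. Table 4-1 reaches discontinuation only at the third reduction; the other route is the 3-week limit, which Section 6.3.1 and Table 4-2 share.
- *That several of the 10 patients would be affected.* The rates in Sections 1.3 and 1.5 (neuropathy 10% to 26%, thrombocytopenia 28% to 34%, rash about 50%) are all-grade rates in oncology patients on other doses or combinations. They do not give the frequency of Grade 2 events that delay a cycle by more than 2 weeks.

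The defence does not remove the three conflicts in the first table under working. Discretion softens the 3-week limit but does not say which table governs, and referring to both tables does not help when they disagree.

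**Conclusion.** The point holds in this form. The written rules give different actions for Grade 2 rash, for Grade 2 neuropathy without pain that delays a cycle by more than 2 weeks, and for Grade 3 nonhematologic toxicity that recovers late. Table 4-2 is also ambiguous about short-lived low counts, although the one-criterion reading is better supported.

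In the illustrated case the difference is 84.9 mg against 108 mg. That rests on one assumed event at cycle 2 and full dosing otherwise. A change in discontinuation status is worth 10 percentage points per patient. The documents do not allow an estimate of how many patients would be affected, and none is offered. The correction should be made before the rules are applied further, because reductions are irreversible, a primary safety variable depends on them, and the change is small. The wrong pointers are editorial on their own, but they make it harder to find which rule applies.

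**What to change.** The sponsor-investigator should:

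1. Reconcile Section 6.3.1, Table 4-2 and Table 4-3 so that each event has one action and one maximum delay. Which clinical rule stands is for the sponsor-investigator to decide.
2. State whether the Table 4-2 criteria cell is one criterion or two.
3. Correct the table references in Sections 4.1, 6.3.1 and 9.1, and the references to Section 6.7 in Table 4-3.
4. Record in the case report form which rule triggered each hold, reduction or stop, so that delivered dose and discontinuations can be interpreted.

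The cost is one protocol amendment to a section, two tables and a few cross-references, plus one data field. It needs no extra visits or patients.

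### Table 4-3 holds ixazomib for painful neuropathy, but its release wording does not require the pain to have gone

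*Combined protocol and SAP*

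**What the plan says.** Table 4-3 has four peripheral neuropathy rows.

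- Grade 1: no action. The adjoining note describes Grade 1 as "asymptomatic; without pain or loss of function; clinical or diagnostic observations only".
- First hold row, triggered by "New or worsening Grade 1 peripheral neuropathy with pain or Grade 2": the action is "Hold study drug until resolution to Grade ≤ 1 or baseline".
- Second hold row, triggered by "New or worsening Grade 2 peripheral neuropathy with pain or Grade 3": the release condition is the same, followed by "Reduce study drug to next lower dose upon recovery".
- Grade 4: discontinue.

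Section 6.3.1 separately sets the conditions for starting a cycle. The non-haematological one begins "All other nonhematologic toxicity (except for alopecia) must have resolved to" and ends at Grade 1 or below, or the patient's baseline. A patient who fails is re-evaluated after a week. Treatment is discontinued after a delay of at most 3 weeks, or at the principal investigator's discretion. Table 4-2 adds a one-level dose reduction when a cycle start slips by more than 2 weeks "due to lack of toxicity recovery as defined in Section 6.3.1".

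Section 6.3 also points outside the protocol: "Ixazomib dose modifying strategies will be implemented as outlined in the IB".

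**The concern.** Pain is what separates no action from a hold at Grade 1, and a plain hold from a hold with dose reduction at Grade 2. A rule that acts on pain should say whether the pain must resolve before dosing resumes. This one releases on grade alone.

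Two things could follow on the literal wording. A hold for painful Grade 1 neuropathy could end the moment it begins. A patient coming down from painful Grade 2 or from Grade 3 could restart at Grade 1 while still in pain, a state for which the row above withholds drug.

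Distal neuropathy is one of the three safety concerns named in the primary objective (Section 2.1), and the pain hold is the first action the table takes for it. How persistent pain is handled can also bear on whether a patient stops treatment. Section 7.1 analyses discontinuation for adverse events as the primary safety endpoint.

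**Working it through.** There is no figure to reproduce. The check compares each trigger with its release and then looks for a pain criterion elsewhere.

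**Step 1: triggers against releases in Table 4-3.**

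| Neuropathy row | Pain named in trigger? | Action | Pain named in release? |
|---|---|---|---|
| Grade 1 | No (the note excludes pain) | None | Not applicable |
| Grade 1 with pain, or Grade 2 | Yes | Hold | No |
| Grade 2 with pain, or Grade 3 | Yes | Hold, then reduce | No |
| Grade 4 | No | Discontinue | Not applicable |

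Pain is named in 2 of 4 triggers and in 0 of 2 release cells.

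**Step 2: suppose Grade 1 can include pain, as the first hold row's trigger says.** A painful Grade 1 event is already at Grade 1 or below, so its release is met at onset. A patient in the second hold row who improves to Grade 1 with residual pain also meets the release. The Section 6.3.1 cycle-start test is met too.

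**Step 3: suppose Grade 1 never includes pain, as the note says.** Both releases then require the patient to be pain-free, which is sensible. But the Grade 1 half of the first hold row's trigger describes something that cannot occur. Pain that does not limit instrumental activities of daily living then fits neither the Grade 1 note nor the Grade 2 note.

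Neither meaning of Grade 1, used consistently, makes the whole table work. A coherent rule needs Grade 1 to allow pain in the trigger and exclude it in the release.

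**Step 4: does the baseline limb help?** No. It is joined by *or*, so it is another way to be released and adds no condition.

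**Step 5: is a pain criterion given elsewhere?**
- Section 6.3.1, cycle-start criteria: grade or baseline only.
- Section 6.2: doses are adjusted to tolerance. This is general discretion.
- Section 4.1: drug is dispensed after adverse events and monthly labs are reviewed. No release criterion is given.
- Section 6.5: worsening neuropathy may be observed, with delays and reductions as the protocol indicates. This leads back to Table 4-3.
- The IB: named in Section 6.3 as a source, but not among the documents.

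No supplied text states when pain releases the hold.

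**The case against.** The strongest reply is that the table already answers the question. The Grade 1 note sits directly above the first hold row and excludes pain. Both cells also speak of resolution, and an event cannot have resolved at onset. This is the more natural reading of intent, and it stands as such. It does not remove the conflict, because it empties the painful Grade 1 trigger.

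A second reply is that residual pain after a higher grade is still new relative to a pain-free baseline, so the first hold row would catch it. That is arguable: the trigger does not say what *new or worsening* is measured against, and Section 6.5 does speak of worsening from baseline. But the first hold row releases on the same words, so on the literal reading the patient would be held and released together.

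Third, this is a single-centre study of 10 patients led by a sponsor-investigator with wide discretion, so sites cannot differ in their reading and sensible handling is likely. The IB may also contain the missing criterion. Both points stand. They limit the likely effect and explain why the IB should be checked first, but they do not supply the criterion in the protocol.

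A reader might go further and infer that patients will be re-dosed in pain, or estimate how many from the background neuropathy rates in Section 1.5. The documents do not support that. The rates in Tables 3-2 and 3-3, 21/201 (10.4%) and 45/173 (26.0%), come from oncology patients, cover all grades and do not separate painful Grade 1. Any count of extra doses would rest on an assumed duration of pain and on the less natural reading.

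**Conclusion.** The point holds as an internal inconsistency in a stated safety rule. Pain triggers or escalates action in two neuropathy rows, and neither release says that it must have gone. Read literally, the release can void the hold at onset or permit a restart in pain after painful Grade 2 or Grade 3. The Grade 1 note suggests this was not intended.

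Probably few patients would be affected, and no number of patients or doses is claimed. Sample size and the efficacy analysis are untouched. The conclusion rests on the supplied text alone. If the IB states a pain-free release, what remains is to bring Table 4-3 into line with it. The wording is worth correcting because the correction is small and the rule concerns a named primary safety outcome.

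**What to change.** 1. Check the IB. If it gives a pain-free release, use its wording.
2. Otherwise change the release in both hold rows to *Grade ≤ 1 without pain, or baseline*. Keeping the baseline limb protects patients who enter with Grade 1 neuropathy, which exclusion 9 in Section 5.2 allows.
3. Label the no-action row *Grade 1 peripheral neuropathy without pain* and leave its descriptor as it is. Deleting the pain-free wording from the descriptor would look tidy but do harm: with Section 6.3.1 unchanged, painful Grade 1 would pass the cycle-start test, and the delay limit that the natural reading now provides would be lost.
4. State that an active Table 4-3 neuropathy hold also blocks the start of a new cycle under Section 6.3.1, with the existing 3-week limit or principal investigator discretion applying. Say in the same sentence whether the Table 4-2 reduction after more than 2 weeks also applies. It would on the pain-free reading, because Table 4-2 uses the Section 6.3.1 definition of recovery, and reduced doses may not be re-escalated.

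The cost is one wording amendment with no added procedures. A patient with persistent new or worsening painful Grade 1 neuropathy may miss up to 3 doses per 28-day cycle (days 1, 8 and 15), and under step 4 may reach the 3-week limit unless the investigator decides otherwise.
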